### 13.5 Secondary Objectives, Endpoints, Analysis Plans

For Objective 1.2.1, baseline descriptive statistics will be compared by intervention arm using chi-square tests for categorical variables and ANOVA for continuous variables. Due to randomization, we do not anticipate differences by intervention arm; if they are found, we will adjust for them in the analyses for Objectives 1.2.1, 1.2.2, 1.2.3, and 1.2.4. The Working Alliance Inventory will be summarized using descriptive statistics.

Depression and anxiety outcomes (PHQ-9 and GAD-7) will be analyzed using mixed-model analysis of covariance (ANCOVA) to account for intra-individual correlations among longitudinal measures. The model will contain terms for the intervention group, baseline value of the outcome, therapist or site staff person completing check-in calls, psychotropic medications use, a time effect (mid-, post-intervention), and the time by intervention interaction term (to test whether the intervention effects vary by time). Because participants may exhibit moderate or severe levels of either depression or anxiety, we will create a combined variable that indicates if a participant had moderate/severe depression or anxiety at mid- or post-intervention. Each stepped-care telehealth group will be compared with EUC using a GEE approach with a logit link to determine if rates of the combined outcome differ at mid- or post-intervention. Other outcome measures (sleep disturbance, fatigue, fear of recurrence, cancer-related distress, and quality of life) will be analyzed using ANCOVA at week 13 to meet objective 1.2.2.

For Objective 1.2.3, we will calculate total cost of the stepped-care telehealth (low intensity, high intensity) and the EUC interventions and average cost/survivor screened and randomized to each trial arm. Total cost includes costs of intervention implementation and health care costs for each participant.

Implementation costs will be determined using data on time spent on intervention activities reported in the tracking logs. Time spent on the intervention includes i) training personnel to screen and deliver the intervention including time of trainer and trainees; ii) time spent by interventionists on intervention activities, including screening, scheduling and delivering the phone sessions, and documenting contacts/progress; iii) phone charges; and iv) other supply costs (e.g., CBT workbooks). Cost of time will be valued using wage rates based on national averages for research staff and psychotherapists. Other costs (e.g., telephone charges and printed materials) will be valued using project records on expenses incurred. We will sum all costs related to each intervention to obtain the total cost of implementing each. Total costs in each study arm will be dividing by the number of patients served to obtain the average cost per patient. Sensitivity analyses will be conducted to assess how implementation costs vary depending on the inputs used, such as the salaries of interventionists or supervisors.

Health care cost will be determined using data from self-reported utilization of health care services (Cornell Services Index). To calculate the costs related to these health care events, we will use published data on average costs of these events or data from sources such as the Medicare Fee Schedule and/or the Medical Expenditure Panel Survey. We will conduct analyses to examine the impact of the stepped-care interventions on health care utilization and costs: similar to analyses specified above for Objective 1.2.1, we will use linear models with utilization or costs as the dependent variable, and the arm assignment as the independent variable. Because the distribution of costs is usually skewed, we will consider using a generalized linear model with a gamma link.

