### **13.2 Randomization/Stratification**

Participants will be stratified by baseline score  $\geq 15$  on the GAD-7 and/or on the PHQ-9, indicating severe anxiety or depressive symptoms, and by whether they qualified for the study by the GAD-7, PHQ-9, or both. Participants with moderate symptoms only (8-14 on the PHQ-9 and  $< 15$  on the GAD-7 or 10-14 on the GAD-7 and  $< 15$  on the PHQ-9) will be randomized to either the low-intensity stepped-care telehealth or to the enhanced usual care (EUC control) with equal probability. Participants with severe symptoms will be randomized to either the high-intensity stepped-care telehealth intervention or the EUC control with equal probability. Participants randomized to the low-intensity stepped care telehealth arm who experience increased symptoms at week seven and now experience severe level of symptomatology will receive the high-intensity intervention (see Section 7.1). Analysis will proceed as intent-to-treat using

their initial stepped-care telehealth assignment; we do not anticipate that many people will change from moderate to severe during the study. We anticipate enrolling 45 patients in the stepped-care telehealth intervention and 45 in the enhanced usual care group. We will enroll 50 participants in the moderate symptom strata, and 40 participants in the severe symptom strata. Block sizes will be chosen randomly to ensure that future assignments cannot be inferred from previous ones.

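### Beyond the fixed core of the PHQ-9/GAD-7 model, extra covariates are picked by baseline tests between randomised arms, and no main model names the stratification factors

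*Combined protocol and SAP*

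**What the plan says.** Section 13.5 begins the secondary analyses with a baseline comparison: "baseline descriptive statistics will be compared by intervention arm using chi-square tests for categorical variables and ANOVA for continuous variables". It then gives the rule: "Due to randomization, we do not anticipate differences by intervention arm; if they are found, we will adjust for them in the analyses". The rule is applied to Objectives 1.2.1 to 1.2.4. No significance threshold and no list of variables to be tested is given. Sections 1.2 and 13.1.2 contain three secondary objectives, so Objective 1.2.4 does not exist.

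What is fixed in advance differs by model:

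- **PHQ-9 and GAD-7 mixed model:** "The model will contain terms for the intervention group, baseline value of the outcome, therapist or site staff person completing check-in calls, psychotropic medications use", plus time and time by intervention.
- **Combined moderate/severe indicator (GEE, logit link):** each stepped-care group is set against EUC; no covariates are named.
- **Sleep, fatigue, fear of recurrence, cancer-related distress, quality of life:** "will be analyzed using ANCOVA at week 13 to meet objective 1.2.2"; no covariates are named.
- **Utilization and cost:** "we will use linear models with utilization or costs as the dependent variable, and the arm assignment as the independent variable". The text calls this similar to the Objective 1.2.1 analyses but names only arm.

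Section 13.2 stratifies randomisation by severity (15 or more on either scale) "and by whether they qualified for the study by the GAD-7, PHQ-9, or both". Neither factor is a named term in any of these models. Severity returns only as an exploratory subgroup in Section 13.6.

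**The concern.** The plan itself expects no baseline differences because of randomisation. A test that finds one therefore identifies a chance difference, not a variable that predicts outcome. Letting the test choose covariates makes the estimate and its interval depend on a preliminary look at the data, and may put non-prognostic variables into a model with about 72 completers.

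The stratification factors are the reverse case. They are cut-points of the outcome scales, so they are likely to be prognostic, and the design forces them to balance. A balance test will pass over them. Stratifying and then leaving the strata out tends to give a standard error that is too large for the design used.

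Section 13.3 gives effect sizes for a larger trial as one basis for N = 90. An effect and residual variance that are conditional on luckily chosen covariates are hard to carry forward.

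**Working it through.** **1. The plan's own precision figure.** Inputs from Section 13.3: 36 per group after 20% dropout from 45; SDs of change 5.8 and 4.2.

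- Half-width = 1.96 × √(2/36) = 0.462 SD, against 0.46 stated.
- In points: 0.462 × 5.8 = 2.68 (PHQ-9) and 0.462 × 4.2 = 1.94 (GAD-7), against 2.7 and 1.9.

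The figure reproduces. It uses no covariates, so this point does not change it.

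**2. Chance selection.** P(at least one) = 1 − (1 − α)^k for k independent tests. Neither α nor k is stated. Section 7.4 lists at least ten baseline measures before counting separate demographic items or SF-36 subscales, so k of 10 to 20 is a reasonable assumption.

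| k | α = 0.05 | α = 0.10 |
|---|---|---|
| 10 | 1 − 0.95^10 = 40% | 65% |
| 15 | 1 − 0.95^15 = 54% | 79% |
| 20 | 1 − 0.95^20 = 64% | 88% |

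The expected number selected at 0.05 is 0.5, 0.75 and 1.0. Correlation among the measures would lower the chance of at least one selection.

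**3. Stratification factors, stepped care v EUC.** Inputs from Section 13.2: 50 moderate and 40 severe, equal allocation, two severity levels × three qualifying categories = 6 strata, random block sizes. Assumed: four sets of block sizes between 2 and 8, and two mixes of qualifying scale. Simulated stratified blocked randomisation, 8 settings × 20,000 = 160,000 trials, Pearson chi-square at 0.05:

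- Either factor selected: 0 of 160,000.
- Smallest p-value seen: 0.20 for severity, 0.30 for qualifying scale, 0.39 for the six cells.
- Without stratification, the selection rate is about 5%.

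**4. The same factor on a three-arm table.** If *arm* means low intensity, high intensity and EUC, the design gives moderate/severe counts of 25/0, 0/20 and 25/20. Expected counts are 13.89/11.11, 11.11/8.89 and 25/20. The rows contribute 20, 25 and 0, so chi-square = 45.0 on 2 df, p = 1.7 × 10⁻¹⁰. Severity would always be selected.

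**5. What test selection does to the estimate.** Simulation with 36 per group, outcome SD 1, 10 or 20 candidate covariates of which three are prognostic with joint R² of 0.3 or 0.5 (assumed), 6,000 runs per setting:

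| Adjustment | Mean reported SE | Type I error |
|---|---|---|
| None | 0.234 to 0.235 | 0.047 to 0.053 |
| Test-selected | 0.236 to 0.242 | 0.036 to 0.043 |
| Pre-specified | 0.201 (R² 0.3); about 0.17 (R² 0.5) | 0.045 to 0.050 |

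Hand check: √(2/36) = 0.236 unadjusted; × √0.7 = 0.197; × √0.5 = 0.167. Test selection gains nothing over no adjustment and is conservative.

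For the strata themselves, if they explain a share R² of the variance left after the model's other terms, omitting them overstates the standard error by about 1/√(1 − R²). The documents give no such R², so no figure is attached.

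**The case against.** The strongest reply has four parts.

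- **The PHQ-9/GAD-7 model is largely pre-specified.** Baseline score, the person delivering therapy or calls, psychotropic use and the time terms are fixed, so the tests can only add to them. This stands. The baseline score also carries part of the severity information, so the gain from adding strata is smaller there. It does not carry the qualifying scale, or severity reached on the other scale.
- **The selection argument depends on which arms are compared.** This stands. Two groups is the more natural reading (45 v 45 in Section 13.2, 36 per group in Section 13.3), but Section 13.5 also treats low and high intensity separately, and there severity would always be selected. The ambiguity does not rescue the rule: a main prognostic factor is in or out according to a word the plan does not define.
- **The percentages rest on assumptions.** Threshold, number of tests and independence are all assumed, and the chance of a selection is not itself a measure of harm. This stands; they are an illustration.
- **The stakes are limited.** Section 13.8 says the effect analyses are for planning, not for showing efficacy. This stands and caps the severity. Planning is nevertheless what these estimates are for.

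A reader might also infer that the GEE comparison of each stepped-care group with EUC is confounded by severity. That would follow only if EUC were pooled across strata, and the documents do not say whether it is.

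**Conclusion.** The point holds in this limited form. Outside the fixed core of the PHQ-9/GAD-7 model, covariates for the secondary analyses are chosen by chance. The stratification factors are in no main model, and for stepped care v EUC the rule would essentially never bring them in.

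The effect is moderate: lost precision and an unpredictable model in secondary planning estimates. The 40%, 54% and 64% assume α = 0.05 and independent tests. The standard-error comparison assumes R² of 0.3 to 0.5, and the gain would be smaller where the baseline score already does the work.

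Three stronger readings are not supported:

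- That all covariates are test-selected: Section 13.5 fixes a core for PHQ-9 and GAD-7.
- That false positives are inflated: simulated type I error under the rule was 0.036 to 0.043, below nominal.
- That the feasibility conclusions or the 0.46 SD half-width are affected: neither uses these covariates.

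**What to change.** In Section 13.5:

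1. Delete the test-then-adjust rule and present baseline characteristics by arm descriptively, without tests. What *arm* means then no longer decides which covariates enter.
2. Pre-specify the covariates for every secondary model under Objectives 1.2.1 to 1.2.3, including the GEE: baseline value of the outcome where collected, severity stratum, qualifying measure (GAD-7, PHQ-9 or both) and baseline psychotropic use. For the GEE, the entry criteria make the combined indicator positive for everyone at baseline on the Section 3 cut-offs, so that baseline term drops out.
3. Leave the therapist/staff term in the PHQ-9/GAD-7 model as it is; it is a separate matter.
4. Remove or define the reference to Objective 1.2.4.

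The cost is SAP wording and a few degrees of freedom: one for severity, two for qualifying measure and, where not already present, one for psychotropic use, out of about 72 completers. No data collection changes.

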## **4. PARTICIPANT SELECTION**

### **4.1 Inclusion Criteria**

- 4.1.1.** Age  $\geq 18$  years
- 4.1.2.** Score  $\geq 10$  on the GAD-7 and/or a score  $\geq 8$  on the PHQ-9, indicating clinically significant anxiety or depressive symptoms, respectively.
- 4.1.3.** Past history of treated (newly diagnosed or recurrent) breast, colorectal, prostate, gynecologic (only uterine and cervical) cancers (Stage I, II, or III) or any stage lymphoma (Hodgkin's or non-Hodgkin's).
- 4.1.4.** 6-60 months post-treatment (surgery, chemotherapy, radiation therapy, and/or maintenance therapies) for cancer. Time frame applies to most recent completion of treatment if participant had a cancer recurrence. It is acceptable to be on hormonal therapies.
- 4.1.5.** Participant resides in California, Georgia, Illinois, Kansas, Michigan, Minnesota, Missouri, New Mexico, North Carolina, North Dakota, South Carolina, Virginia, Tennessee, or Wisconsin.
- 4.1.6.** Study-trained therapist in the state where the participant resides.
- 4.1.7.** Must be able to speak and understand English.
- 4.1.8.** Must have access to a telephone. If a patient does not have access to a phone or has difficulty paying for minutes for a mobile phone, the research team should contact the Wake Forest investigators or site coordinators to arrange for assistance.

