### 13.3 Sample Size

The sample size (N=90) is based on goals of estimating retention, recruitment, adherence and accrual rates and effect sizes to inform design of a larger efficacy trial. If the drop-out rate is  $>30\%$ , a larger study may not be feasible. With N=90, we are confident that this rate will be  $\leq 30\%$  when the observed drop-out rate is as large as 22% (upper limit of the one-sided 95% CI is 29.2%). Similarly, the lower limit of a one-sided 95% confidence interval for the recruitment rate can be estimated within 8.2% of the observed rate if we approach at least 100 participants to recruit 90, and the lower limit of a one-sided 95% confidence interval for the adherence can be estimated within 8.7% of the observed rate with N=90. Using the normal approximation to the Poisson, we can estimate the lower limit of the one-sided 95% confidence interval of the accrual rate within approximately 2 people per month if the observed rate is 11 people per month. To compare differences between the groups on changes in the PHQ-9 and GAD-7 scores, we can estimate the intervention effect within  $\pm 0.46$  SD with a sample size of 36/group (stepped-care telehealth, enhanced usual care), allowing 20% dropout of the 45/group randomized. This corresponds to 2.7 points on PHQ-9 and 1.9 points on GAD-7 using SDs from studies of change in the measures of 5.8 and 4.2 points, respectively.

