### **13.6 Exploratory Objectives, Endpoints, Analysis Plans**

We will perform stratified subgroup analysis of the outcomes in Objectives 1.2.1 and 1.2.2. by gender, age, race/ethnicity, stratification arm (moderate, severe), and psychotropic medication use at baseline to meet Objective 1.3.1 using ANCOVA at week 13. To analyze Objective 1.3.2, we will use a mediation approach to examine whether expectancy ratings mediate the relationship between the intervention and the outcomes of interest (PHQ-9, GAD-7, or the combined outcome) at the intervention mid-point or end. First, we will examine whether the expectancy rating score is a significant predictor of the outcome in the mixed-model analysis of covariance (ANCOVA) model with terms for the expectancy rating score, baseline value of the outcome, therapist or site staff person conducting check-in calls, psychotropic medications use, a time effect (mid-, post-intervention), and the time by intervention expectancy score term (to test whether the expectancy score effects vary by time). Then we will fit the same model with the intervention effect, expectancy rating score, and their interactions with each other and time. If the effect for the mediator is significant in this model and the parameter estimate of the intervention effect is smaller than in the analysis of Objective 1.2.1 it will indicate evidence of mediation.

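### Randomization is stratified by qualifying scale (GAD-7, PHQ-9 or both), but the PHQ-9 and GAD-7 analyses never use that factor, so no effect size is planned for people elevated on the scale being analysed

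*Combined protocol and SAP*

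**What the plan says.** Section 4.1 admits a participant with GAD-7 of at least 10 and/or PHQ-9 of at least 8, "indicating clinically significant anxiety or depressive symptoms, respectively". Section 13.2 stratifies randomization by severity "and by whether they qualified for the study by the GAD-7, PHQ-9, or both". The only mix it states is by severity: "We will enroll 50 participants in the moderate symptom strata, and 40 participants in the severe symptom strata".

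For the outcomes, Section 13.5 says "Depression and anxiety outcomes (PHQ-9 and GAD-7) will be analyzed using mixed-model analysis of covariance (ANCOVA". The listed terms are intervention group, baseline value of the outcome, therapist or caller, psychotropic medication use, time, and time by intervention. Qualifying scale is not among them. Section 13.7 includes all consenting participants in these analyses. Section 13.6 plans subgroups by gender, age, race/ethnicity, "stratification arm (moderate, severe), and psychotropic medication use at baseline to meet Objective 1.3.1"; qualifying scale is again absent.

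Section 13.5 does recognise mixed entry. It adds a binary outcome for moderate/severe depression or anxiety at mid- or post-intervention, analysed by GEE with a logit link.

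Objective 1.2.1 seeks preliminary data on efficacy and variability, and Section 13.3 says the sample size serves, among other goals, "effect sizes to inform design of a larger efficacy trial".

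**The concern.** Someone who enters on the GAD-7 alone has a PHQ-9 of 0–7. Someone who enters on the PHQ-9 alone has a GAD-7 of 0–9. Section 13.5 gives one arm effect per scale, averaged over people who have that symptom at entry level and people who do not. That average depends on the entry mix of this particular trial.

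The trial randomizes within the variable that separates these groups, so an estimate by qualifying scale would be a properly randomized comparison. The plan does not produce one. A later team that wanted to enrol on one scale, or expected a different mix, would have no prespecified effect or SD to work from.

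**Working it through.** **Inputs.** From Section 13.3: 45 per group randomized, 20% dropout, SDs of change 5.8 (PHQ-9) and 4.2 (GAD-7), precision ±0.46 SD. From Section 4.1: cut-offs 8 and 10. Not in the documents, so varied: *s*, the share at or above a given scale's cut-off, and *f*, the effect in sub-threshold entrants relative to that in qualifiers.

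**The plan's own figure.** 45 × 0.80 = 36 per group. Half-width = 1.96 × √(2/36) = 0.462 SD. Then 0.462 × 5.8 = 2.68 and 0.462 × 4.2 = 1.94. Section 13.3 says "This corresponds to 2.7 points on PHQ-9 and 1.9 points on GAD-7", so the figure reproduces (two-sided 95%, normal quantile) and is not in error. It applies to the all-participant comparison.

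**Pooled effect as a fraction of the effect in qualifiers:** *s* + (1 − *s*) × *f*.

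**Half-width among qualifiers only:** 1.96 × √(2/(36*s*)) SD.

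| *s* | n per group | Half-width (SD) | PHQ-9 points | GAD-7 points | Fraction, *f* = 0 | Fraction, *f* = 0.5 |
|---|---|---|---|---|---|---|
| 1.0 | 36 | 0.46 | 2.7 | 1.9 | 1.00 | 1.00 |
| 0.9 | 32.4 | 0.49 | 2.8 | 2.1 | 0.90 | 0.95 |
| 0.7 | 25.2 | 0.55 | 3.2 | 2.3 | 0.70 | 0.85 |
| 0.5 | 18 | 0.65 | 3.8 | 2.7 | 0.50 | 0.75 |

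If *f* = 1 the fraction is 1.00 whatever the mix.

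**Which scale is more exposed.** An illustrative simulation assumed bivariate normal scores before entry (PHQ-9 means 6–10, SD 5.5; GAD-7 means 5–9, SD 5; correlation 0.5–0.75), rounded and truncated to each scale, with the and/or entry rule applied. All of these inputs are assumptions. About 5–13% of entrants fell below the PHQ-9 cut-off and 35–59% below the GAD-7 cut-off.

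- With a constant latent shift of 0.46 SD of change and scores stopped at zero, the pooled effect was 96–99% (PHQ-9) and 86–96% (GAD-7) of that in qualifiers.
- With benefit proportional to baseline, it was 92–97% and 66–83%.

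**Do other planned analyses fill the gap?**

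- Baseline value enters as a main effect only. It adjusts for level but leaves one effect averaged over everyone.
- The combined outcome is binary and yields no PHQ-9 or GAD-7 effect or SD among people elevated on that scale.
- The moderate/severe subgroup does not identify the qualifying scale. GAD-7 16 with PHQ-9 3 is severe under Section 13.2, yet below the PHQ-9 cut-off.

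**The case against.** **The pooled effect may be exactly what is wanted.** Section 2.2 describes a later trial of distress in cancer survivors, and the objectives define distress as anxiety and/or depressive symptoms. If that trial keeps and/or entry with a similar mix, the all-randomized effect is the right planning figure and is not biased for it. This stands. Using qualifier-only figures there would do harm. With 80% power planned on the qualifiers' effect and the same SD, true power is Φ(2.80*r* − 1.96), where *r* is the fraction above: at *r* = 0.85, Φ(0.42) ≈ 66%; at *r* = 0.70, Φ(0.00) = 50%. The documents do not, however, fix the later trial's entry rule.

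**Any gap is small against this trial's precision.** Taking an assumed 0.5 SD effect in qualifiers, the pooled effect is 0.425 SD at *r* = 0.85 and 0.35 SD at *r* = 0.70, gaps of 0.075 and 0.15 SD against ±0.46. This also stands, and it is why the breakdown should be descriptive.

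**Feasibility is the primary objective, and both scales are collected on everyone,** so the breakdown could be made later. True, but prespecifying it costs little.

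**Stronger readings the documents do not support.** A reader might infer that a floor demonstrably biases the effect sizes downward. Nothing shows this: *s* and *f* are not given, sub-threshold entrants can still score up to 7 or 9, and an arm difference can also arise from worsening under usual care, for which Sections 5.5 and 11.3.1 make provision. A reader might also set low entry scores against the 2.7 points in Section 13.3. That number is the half-width for a between-group mean difference, not a change that an individual must achieve.

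**Conclusion.** The gap is real but limited. A factor used to stratify randomization is missing from both the PHQ-9/GAD-7 model terms and the subgroup list, and nothing else planned gives a scale-specific effect and SD among people with that symptom.

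Whether the pooled effect is smaller than the effect in those people depends on two unknowns. It is smaller only if sub-threshold entrants gain less (*f* < 1). At *s* = 0.7 it would be 70–85% of the qualifiers' effect for *f* between 0 and 0.5; at *s* = 0.9, 90–95%. Under the simulation's assumptions the GAD-7 is more exposed than the PHQ-9. The plan's ±0.46 SD is correct for what it describes. The point bears on a secondary objective and leaves the feasibility endpoints untouched.

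**What to change.** In Section 13.5:

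- Keep the all-randomized estimate as the main one and add the qualifying-scale stratum as a model term. The term alone brings the model into line with the randomization; it does not give separate effects.
- Report descriptively, with intervals, each scale's arm effect and SD among those at or above its entry cut-off at baseline (PHQ-9 ≥ 8; GAD-7 ≥ 10).
- State that the pooled estimate is the planning figure if the later trial keeps and/or entry, and that the scale-specific estimate is the planning figure only if the later trial enrols on that scale.

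In Section 13.6, add qualifying scale to the subgroup list.

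The cost is SAP wording and a few extra tables from data already collected; trial conduct does not change. The downside is that the scale-specific estimates will be imprecise, and the report should say so.
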